4.6 Interim Analyses

Interim analyses will be performed at the request of the data monitoring committee and at the request of the sponsor to enable reporting of adequate data at selected time points during the course of the trial. Descriptive statistics alone will be used for the interim analyses.

Clinical Trial Protocol

Trial ID: CT-AMT-060-01

uniQure

5. Schedule of Trial Procedures

Subjects will attend a screening visit (Visit 1) at a maximum of 6 weeks prior to the anticipated dosing visit (Visit 2). When the screening visit blood sample analysis results from the local and central laboratory are available, and it is confirmed that the subject is fulfilling the trial eligibility criteria, the dosing visit can occur provided that the intra- and inter-cohort staggering principles are adhered to (see [Section 10.1](#)). Sufficient time should be allowed for IMP shipment and preparation.

In case the subject no longer fulfils the eligibility criteria at the time of the dosing visit, re-screening is allowed as detailed in [Section 10.2.1](#).

After IMP administration, subjects will be monitored for tolerance to the IMP and detection of potential immediate AEs at the clinical trial site for 24 hours (overnight stay). Thereafter, subjects will be followed with respect to safety and efficacy parameters for 5 years (260 weeks) as follows:

- Twice weekly up to week 12
- Every 2nd week from week 12 to week 26
- Every 13th week from week 26 to week 156 (6 months to 3 years)
- Every 26th week from week 156 to week 260 (3 years to 5 years)

Clinical procedures to be performed in the period up to week 26 are listed in [Table 5-1](#).

Clinical procedures to be performed after week 26 and up to week 260 are listed in [Table 5-4](#).

Laboratory parameters to be measured in the period up to week 26 are listed in [Table 5-2](#).

Laboratory parameters to be measured after week 26 and up to week 260 are listed in [Table 5-5](#).

Clinical procedures to be performed in relation to IMP administration and the subsequent 24 hour observation period at the clinic (Visit 2) are listed in [Table 5-3](#).

Adjustments to the visit location or schedule may be made to accommodate safety concerns and restrictions due to the Coronavirus Disease 2019 (COVID-19) pandemic. In all cases, subjects will be kept informed as much as possible, of changes to the study and monitoring plans that could impact them.

Clinical Trial Protocol

Trial ID: CT-AMT-060-01

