- 5) Sampling applicable for the individual subject and for a specific matrix, only until 3 consecutive negative samples have been detected for the subject in that particular type of matrix. Based on the wish of the subject, faeces and semen samples can be collected at home prior to attending the visit (at the visit day or at the day before the visit day).
- 6) Haemoglobin, haematocrit, platelet count, red blood cells, white blood cells with differential count (all expressed in % as well as in absolute numbers).
- 7) aPTT and PT (INR).
- 8) Serum electrolytes (sodium, potassium), creatinine, gamma-glutamyltransferase (γ GT), aspartate aminotransferase (AST), alanine aminotransaminase (ALT), alkaline phosphatase (ALP), CRP, albumin, total bilirubin, glucose (non-fasting).
- 9) pH, protein, blood, leucocyte esterase, glucose.
- 10) Only if separate informed consent is given by the subject, see also [Section 12.3.11](#).

6. Introduction and Rationale

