The intravenous administration of AAV8-hFIX did not cause any unexpected or serious adverse events (SAEs). A single intravenous infusion of vector in all 10 subjects with severe haemophilia B resulted in a dose-dependent increase in circulating FIX to a level that was 1 to 6% of the normal value over a median period of 3.2 years, with observation ongoing. In the high-dose group, a consistent increase in the FIX level to a mean (\pm standard deviation [SD]) of $5.1 \pm 1.7\%$ was observed in all 6 subjects, which resulted in a reduction of more than 90% in both bleeding episodes and the use of prophylactic FIX concentrate (Nathwani et al., 2014). Of the 7 subjects who were receiving FIX concentrate prophylactically at the time of vector infusion, 4 were able to discontinue therapy without having spontaneous bleeding. Vector DNA was found in excretions and secretions, but was cleared around 6 weeks after administration. A transient increase in the mean alanine aminotransferase level occurred between week 7 and week 10 in 4 of the 6 subjects in the high-dose group but resolved over a median of 5 days (range, 2 to 35) after prednisolone treatment. None of the 10 subjects have developed inhibitors to FIX.

Clinical Trial Protocol

Trial ID: CT-AMT-060-01

The elevation of serum aminotransferase levels appeared to be different to what had occurred in the previous liver-directed AAV clinical trial, by manifesting itself later following vector administration. The causal relationship and the significance of the liver enzyme perturbations currently remain unclear. It has been speculated that the liver enzyme increase is related to a specific T cell reactivity (CTL). Two subjects at the lower dose level of AAV8 presented with high levels of CTL reactivity to capsid as observed in peripheral blood mononuclear cells without concurrent elevation of liver enzyme levels.

The clinical results published by Nathwani (Nathwani et al., 2011 and Nathwani et al., 2014) has invigorated the field and, currently, 3 ongoing clinical trials that also apply AAV based liver-directed gene therapy approaches for the treatment of haemophilia B are registered on www.clinicaltrials.gov (NCT01620801; NCT00979238; NCT01687608).

Optimized AAV gene therapy for treatment of haemophilia B

AAV5-hFIX has been designed to further optimize the risk/benefit balance for haemophilia B by balancing adequate potency and longevity of expression with any potential risk, see [Section 6.5](#).

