# Statistical analyses and presentation of data

# 4.1 General Considerations

All reporting will be made for the Full Analysis Set. Reporting may also be made for other analysis populations (PP Analysis Set), or subgroups of patients based on for example genotype.

Data will be presented in tables and listings following the principles in ICH E3 guideline regarding (structure and content of clinical reports). On the listings, cohort will appear in a separate column and the listings will be sorted by cohort/dose and patient ID within cohort/dose. In the tables data from each cohort/dose will be presented in separate columns. For selected endpoints data will also be presented graphically.

All data will be listed, including unused and spurious data. Imputation of missing or partial data will not be done unless explicitly described. In the case of imputation of missing data, both the original missing or partial data and the imputed values will be listed. Continuous data will be shown in listings with the same precision as captured.

Summary tables will show the number of non-missing values

Numerical data will be presented in summary tables by number of patients, arithmetic mean, median, standard deviation, minimum and maximum and CV (%). Categorical data will be presented by number and percent of patients as well as the number of events (where applicable).

Patient level summaries (listings) will be presented adjusted for observation time where applicable. This includes but is not limited to the annualized rate of selected signs and symptoms and annualized bleeding rate.

In general, laboratory parameters will be presented by visit and will include categorization of parameters into low/normal/high where applicable. For some of the laboratory parameters a measurement of '< x' (x being a numerical value) are occasionally registered. In such a case a value equal to  $0.5^*x$  is used when summary tables are generated, whereas the '< x' will be reported in listings. This recalculation for use in summary tables will also be documented in the ADRG.

The distance in days between a measurement/event and the trial drug administration date is calculated as follows:

- If date(measurement/event) < date(trial drug administration): Distance in days = date(measurement/event) – date(trial drug administration)
- If date(measurement/event) >= date(trial drug administration): Distance in days = date(measurement/event) – date(trial drug administration) + 1

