## 4.5.2 Secondary Safety Endpoints

All data described in this section will simply be presented in listings. The listings will include calculated change from baseline (Visit 2, day 1) where applicable.

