#### 4.5.2.1 Vector DNA in Semen, Blood, Saliva, Nasal Secretions, Urine and Faeces

Sampling of the following types of matrix will be performed to determine Vector DNA levels: Blood, saliva, nasal secretions, urine, faeces and semen. Sampling time points are given as: Visits 2-35.

Sampling should continue for the individual patient and for a specific matrix until 3 consecutive negative samples have been detected for the patient for that particular type of matrix.

All data will be listed. Furthermore, each individual patient profile will be presented graphically per matrix.

Time to first shedding negative will be defined for each type of matrix and each patient as the post treatment time point where a negative result is measured for the first time in a consecutive order of 3 or more time points with a negative result. Negative result is defined as a result of either '0' or 'LOD'. The time to first shedding negative will be flagged on the above-mentioned listings and will also be summarized.

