				1 490 00 01 00
Table 14.3.7.2 Summary of tir	ne to first shedding ne	gative (days) - Vector DNA - F	ull analysis set	
	Cohort 1 (N=x)	Cohort 2 (N=x)	Total (N=x)	
Vector DNA Blood (copies/mL)				
n	x (xxx) x	x (xxx) x	x (xxx) x	
Mean (SD)	x (xxx) x	x (xxx) x	x (xxx) x	
Median	x (xxx) x	x (xxx) x	x (xxx) x	
Min ; Max	x (xxx) x	x (xxx) x	x (xxx) x	
Vector DNA Faeces (copies/mg)				
n	x (xxx) x	x (xxx) x	x (xxx) x	
Mean (SD)	x (xxx) x	x (xxx) x	x (xxx) x	
Median	x (xxx) x	x (xxx) x	x (xxx) x	
Min ; Max	x (xxx) x	x (xxx) x	x (xxx) x	
Vector DNA Nasal Secretion (copies po	er swab)			
n	x (xxx) x	x (xxx) x	x (xxx) x	
Mean (SD)	x (xxx) x	x (xxx) x	x (xxx) x	
Median	x (xxx) x	x (xxx) x	x (xxx) x	
Min ; Max	x (xxx) x	x (xxx) x	x (xxx) x	
Vector DNA Saliva (copies/mL)				
n	x (xxx) x	x (xxx) x	x (xxx) x	
Mean (SD)	x (xxx) x	x (xxx) x	x (xxx) x	
Median	x (xxx) x	x (xxx) x	x (xxx) x	
Min ; Max	x (xxx) x	x (xxx) x	x (xxx) x	

N: Number of patients in Full Analysis Set (FAS). n: Number of patients who have met the criterion for shedding negative.

First shedding negative is defined for a specific matrix when 3 consecutive negative samples have been detected for the patient for that particular type of matrix.

Cohort 1: AAV5-hFIX 5.0 x 10^12 gc/kg, Cohort 2: AAV5-hFIX 2.0 x 10^13 gc/kg

UniQure/AMT/CT-AMT-060-01/current - tab\_shed\_neg.sas/tab\_shed\_neg.rtf/10jan2018

Sponsor: uniQure biopharma B.V Trial ID: CT-AMT-060-01		Date 27MAY2021		Final Version 05
EudraCT No: 2013-00557942-42		Table Shells		Page 59 of 66
Table 14.3.7.2 Summary of time to first	shedding negative (days) - Vo	ector DNA - Full analysis set		
	Cohort 1 (N=x)	Cohort 2 (N=x)	Total (N=x)	
Vector DNA Semen (copies/mL)				
n	x (xxx) x	x (xxx) x	x (xxx) x	
Mean (SD)	x (xxx) x	x (xxx) x	x (xxx) x	
Median	x (xxx) x	x (xxx) x	x (xxx) x	
Min ; Max	x (xxx) x	x (xxx) x	x (xxx) x	
Vector DNA Urine (copies/mL)				
n	x (xxx) x	x (xxx) x	x (xxx) x	
Mean (SD)	x (xxx) x	x (xxx) x	x (xxx) x	
Median	x (xxx) x	x (xxx) x	x (xxx) x	
Min ; Max	x (xxx) x	x (xxx) x	x (xxx) x	

N: Number of patients in Full Analysis Set (FAS). n: Number of patients who have met the criterion for shedding negative.

First shedding negative is defined for a specific matrix when 3 consecutive negative samples have been detected for the patient for that particular type of matrix.

Cohort 1: AAV5-hFIX 5.0 x 10^12 gc/kg, Cohort 2: AAV5-hFIX 2.0 x 10^13 gc/kg

UniQure/AMT/CT-AMT-060-01/current - tab\_shed\_neg.sas/tab\_shed\_neg.rtf/10jan2018

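### SAP Table 14.3.7.2 summarises time to shedding-negative only among patients who cleared; a fully sampled patient who has not cleared by week 260 drops out, and the printed maximum and mean are then too short

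*SAP*

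**What the plan says.** SAP 4.5.2.1 dates the event, per patient and matrix, to the point "where a negative result is measured for the first time in a consecutive order of 3 or more time points with a negative result". It says the resulting time will be flagged in the listings and summarised, and names no method. It gives no value for a patient without such a run.

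The shell for Table 14.3.7.2, which appears more than once in the table-shell document, settles who is counted: "n: Number of patients who have met the criterion for shedding negative". Its rows are n, mean (SD), median and min/max, in days. There is no row for patients who have not met the criterion.

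SAP 4.1 is consistent with this: "Summary tables will show the number of non-missing values", and missing data are not imputed unless a rule is written down. None is written for this variable. The only time-to-event models named anywhere (Protocol 14.2.2) are optional and concern bleeds.

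On sampling, SAP 4.5.2.1 states "Sampling time points are given as: Visits 2-35", that is, up to week 260. Protocol Table 5-5, footnote 5, applies sampling "only until 3 consecutive negative samples have been detected for the subject in that particular type of matrix". A patient still shedding therefore continues to be sampled.

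For the secondary safety endpoints as a group, SAP 4.5.2 says "All data described in this section will simply be presented in listings". For vector DNA, SAP 4.5.2.1 adds individual profile plots and this one summary.

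**The concern.** A patient who has not met the criterion is not an ordinary missing value. If he was sampled throughout, what is known is that his time is long. Dropping him removes the slowest patient from a summary whose purpose is to show how long shedding lasts.

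Vector DNA in six matrices is a named secondary safety endpoint, and Table 14.3.7.2 is its only summary table. The range it prints ends at the slowest patient who cleared. It therefore cannot show persistent shedding, the outcome a reader would most want it to show. What is at stake is the cohort summary, not the data behind it.

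**Working it through.** The plan states no figure for this endpoint, so there is nothing to reproduce. The check has three parts.

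**1. What the visit schedule allows (no distributional assumption).** Post-dose sampling weeks, from Protocol section 5 and Tables 5-2 and 5-5: 1 to 12 weekly; 14 to 26 every 2; 39 to 156 every 13; then 182, 208, 234, 260. Blood, urine, saliva and nasal secretions also have a 24-hour sample, which does not affect the end of the schedule.

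- Three negatives are needed and the event is dated to the first. The latest printable time is thus the third-from-last sample: week 208.
- For a fully sampled patient who has not met the criterion, weeks 208, 234 and 260 are not all negative. If 208 is positive and 234 and 260 are negative, a qualifying run could start at week 234. Every other pattern puts the start at week 260 or later. His time is therefore at least week 234.
- Shortfall in the printed maximum: at least 234 − 208 = 26 weeks (182 days), in nominal weeks. With the ±4-week windows at these visits it is at least 230 − 212 = 18 weeks.
- Because his time exceeds every printed time, omitting him lowers the mean and the maximum. The median stays the same or falls.

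**2. Hypothetical cohort of five.** First negatives at weeks 8, 14, 26 and 52, and one patient fully sampled but not met.

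| | Table as planned | All five |
|---|---|---|
| n | 4 | 5 (4 met, 1 not met) |
| Median | (14 + 26)/2 = 20 | Kaplan-Meier 26 |
| Mean | (8 + 14 + 26 + 52)/4 = 25 | at least (8 + 14 + 26 + 52 + 234)/5 = 66.8 |
| Range | 8 to 52 | 8 to 208+ |

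Kaplan-Meier survival falls to 4/5, 3/5 and 2/5 after weeks 8, 14 and 26, so the median is 26.

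**3. How often a patient would be excluded (assumption).** The documents give no clearance distribution for this vector. Assume exponential clearance with median m weeks and full sampling. The chance of meeting the criterion is p = 1 − 2^(−208/m), and the chance that at least one of five is excluded is 1 − p^5.

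| m (weeks) | p | 1 − p^5 |
|---|---|---|
| 6 | 1.000 | 0% |
| 13 | 1.000 | 0% |
| 26 | 0.996 | 2% |
| 52 | 0.938 | 28% |
| 104 | 0.750 | 76% |

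For the size of the shift I simulated five patients on the actual visit grid (100,000 runs), dating each to the next scheduled visit. The all-five comparison continues the grid every 26 weeks past week 260.

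| m | Expected mean, printed | Expected mean, all five | Typical median, printed | Typical median, all five |
|---|---|---|---|---|
| 26 | 40.6 | 41.4 | 26 | 26 |
| 52 | 66.3 | 81.0 | 52 | 52 |
| 104 | 87.0 | 158.0 | 78 | 104 |

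Under these assumptions the mean is affected materially from about one year. The typical median is unchanged at one year and clearly shorter at two.

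**The case against.** Much can be said for leaving the table alone.

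- **The exclusion is disclosed.** N and n are both defined under the table, so the number not cleared is N minus n. The listings and the profile plots show each patient. With five to seven men per cohort, a non-clearer would be seen directly. This stands, and it is the main reason the priority is low.
- **The evidence points to no effect.** For the AAV8 product, Protocol 6.6.3 reports: "Vector DNA was found in excretions and secretions, but was cleared around 6 weeks after administration". Protocol 6.7 also describes shedding as limited in time. At medians of 6 to 13 weeks the exclusion chance above is 0%. This stands, with the caveat that the 6-week figure comes from another serotype at lower doses.
- **Not every excluded patient is slow.** Someone who withdrew early might have cleared before the printed maximum. A man negative at weeks 208 and 260 with week 234 missed has not met the criterion, yet may have cleared by week 208. This stands: the 26-week statement holds only for complete sampling.
- **No decision depends on the table.** Condom use follows each subject's own semen results (Protocol 9.2, inclusion criterion 5), and no hypothesis is tested.
- **Kaplan-Meier on five patients adds little.** This is partly right. The counts, the label and the marked censored values carry most of the benefit.

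A reader might infer that the table will read short whenever anyone is excluded, or that it conceals persistent shedding. The documents support neither. The direction is certain only for fully sampled patients, and such patients remain visible in other displays. Nor can long clearance be presumed: the 52- and 104-week scenarios are assumptions with no source in the documents. Interim reporting is not a live issue either, because both cut-offs in SAP Appendix 1 (2016 and 2017) predate this SAP version.

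**Conclusion.** The point holds conditionally. If at least one patient in a matrix is sampled on the full schedule to week 260 without three consecutive negatives, the printed maximum is short by at least 26 nominal weeks, the mean is short, and the median is the same or shorter. That follows from the visit schedule alone. If n = N there is no effect. If a patient is excluded through withdrawal or missed samples, the direction is open.

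The frequency cannot be derived from the documents. The 2%, 28% and 76% for true medians of 26, 52 and 104 weeks rest on exponential clearance and complete sampling. The single human figure in the protocol points to the no-effect case. This is a low-priority improvement to one descriptive table. It does not call the shedding data or any individual safety measure into question.

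**What to change.** In SAP 4.5.2.1 and Table 14.3.7.2, for each matrix:

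1. Show the number of FAS patients who met and who did not meet the criterion.
2. Censor those who did not at the last sample that could still have started a run of three (week 208 for a fully sampled patient). Censoring at week 260 would overstate what is known about a man negative only at weeks 234 and 260.
3. Report the Kaplan-Meier median, or 'not reached', and the range with censored values marked, for example 208+.
4. Label any mean and SD as applying only to patients who met the criterion.

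The cost is a sentence or two in the SAP and a few shell rows. The samples are already collected. If every patient clears, the median and range are unchanged. The week-208 limit remains, but becomes visible.

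The downside is small numbers. With about five patients per cohort any interval will be wide, and the median is not reached when fewer than three of five meet the criterion. Under the exponential assumption that has a chance of about 10% at a true median of 104 weeks (p = 0.75: 0.001 + 0.015 + 0.088 for zero, one and two met) and 0.2% at 52 weeks.

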## 14.3.7 Other Safety Observations Displays

	larix
Table Shells	Final Version 05 Page 61 of 66
	Table Shells

### Table 14.3.7.1 Summary of concomitant medications (Other than FIX replacement therapy) by therapeutic grouping - Full analysis set

ATC level 1 ATC level 2	Cohort 1 (N=x) n (%) E	Cohort 2 (N=x) n (%) E	Total (N=x) n (%) E	
Any medication	x (xxx) x	x (xxx) x	x (xxx) x	
Alimentary Tract And Metabolism	x (xxx) x	x (xxx) x	x (xxx) x	
Drugs For Acid Related Disorders	x (xxx) x	x (xxx) x	x (xxx) x	
Drugs Used In Diabetes	x (xxx) x	x (xxx) x	x (xxx) x	
Drugs For Constipation	x (xxx) x	x (xxx) x	x (xxx) x	
Antidiarrheals, Intestinal Antiinflammatory/Antiin	x (xxx) x	x (xxx) x	x (xxx) x	
Antiemetics And Antinauseants	x (xxx) x	x (xxx) x	x (xxx) x	
Drugs For Functional Gastrointestinal Disorders	x (xxx) x	x (xxx) x	x (xxx) x	
Vitamins	x (xxx) x	x (xxx) x	x (xxx) x	
Stomatological Preparations	x (xxx) x	x (xxx) x	x (xxx) x	
Nervous System	x (xxx) x	x (xxx) x	x (xxx) x	
Analgesics	x (xxx) x	x (xxx) x	x (xxx) x	
Psycholeptics	x (xxx) x	x (xxx) x	x (xxx) x	
Anesthetics	x (xxx) x	x (xxx) x	x (xxx) x	
Cardiovascular System	x (xxx) x	x (xxx) x	x (xxx) x	
Agents Acting On The Renin-Angiotensin System	x (xxx) x	x (xxx) x	x (xxx) x	
Lipid Modifying Agents	x (xxx) x	x (xxx) x	x (xxx) x	
Beta Blocking Agents	x (xxx) x	x (xxx) x	x (xxx) x	

N: Number of patients in Full Analysis Set (FAS). ATC Class: Anatomical Therapeutic Chemical Classification.

n: Number of patients with the medication. (%): Percentage of patients with the medication in FAS. E: Number of Medications.

Cohort 1: AAV5-hFIX 5.0 x 10^12 gc/kg, Cohort 2: AAV5-hFIX 2.0 x 10^13 gc/kg

Medication coded with WHO DD version 143E

Sponsor: uniQure biopharma B.V	Date 27MAY2021	larix
Trial ID: CT-AMT-060-01 EudraCT No: 2013-00557942-42	Table Shells	Final Version 05 Page 62 of 66

#### Table 14.3.7.1 Summary of concomitant medications (Other than FIX replacement therapy) by therapeutic grouping - Full analysis set

ATC level 1 ATC level 2	Cohort 1 (N=x) n (%) E	Cohort 2 (N=x) n (%) E	Total (N=x) n (%) E	
Diuretics	x (xxx) x	x (xxx) x	x (xxx) x	
Calcium Channel Blockers	x (xxx) x	x (xxx) x	x (xxx) x	
Antiinfectives For Systemic Use	x (xxx) x	x (xxx) x	x (xxx) x	
Antibacterials For Systemic Use	x (xxx) x	x (xxx) x	x (xxx) x	
Antivirals For Systemic Use	x (xxx) x	x (xxx) x	x (xxx) x	
Vaccines	x (xxx) x	x (xxx) x	x (xxx) x	
Systemic Hormonal Preparations, Excl. Sex Hormones	x (xxx) x	x (xxx) x	x (xxx) x	
Corticosteroids For Systemic Use	x (xxx) x	x (xxx) x	x (xxx) x	
Musculo-Skeletal System	x (xxx) x	x (xxx) x	x (xxx) x	
Antiinflammatory And Antirheumatic Products	x (xxx) x	x (xxx) x	x (xxx) x	
Muscle Relaxants	x (xxx) x	x (xxx) x	x (xxx) x	
Blood And Blood Forming Organs	x (xxx) x	x (xxx) x	x (xxx) x	
Antihemorrhagics	x (xxx) x	x (xxx) x	x (xxx) x	
Blood Substitutes And Perfusion Solutions	x (xxx) x	x (xxx) x	x (xxx) x	
Respiratory System	x (xxx) x	x (xxx) x	x (xxx) x	
Drugs For Obstructive Airway Diseases	x (xxx) x	x (xxx) x	x (xxx) x	

N: Number of patients in Full Analysis Set (FAS). ATC Class: Anatomical Therapeutic Chemical Classification.

n: Number of patients with the medication. (%): Percentage of patients with the medication in FAS. E: Number of Medications.

Cohort 1: AAV5-hFIX 5.0 x 10^12 gc/kg, Cohort 2: AAV5-hFIX 2.0 x 10^13 gc/kg

Medication coded with WHO DD version 143E

Sponsor: uniQure biopharma B.V	Date 27MAY2021	larix
Trial ID: CT-AMT-060-01 EudraCT No: 2013-00557942-42	Table Shells	Final Version 05 Page 63 of 66

